8.6 Safety and Tolerability

The following variables will be summarized and analyzed descriptively for each cohort: number of completed cycles, relative dose intensity, number and percentages of patients with TEAEs, SAEs, TEAEs leading to study drug discontinuation, TEAEs related to the study drug; and the severity of TEAEs based on CTCAE, Version 5.0.

8.7 Clinical Laboratory Evaluations

Key laboratory parameters will be summarized using shift tables, which display a cross-tabulation of the Baseline grade *versus* the highest on-study grade for each laboratory parameter, for each cohort.

All laboratory abnormalities will be classified according to NCI CTCAE, Version 5.0, and summarized by worst grade severity and by treatment.

9 ADMINISTRATIVE PROCEDURES AND STUDY MANAGEMENT

9.1 Investigator Responsibilities

The study will be monitored by employees or representatives of Spectrum. CRAs will monitor each site on a periodic basis and perform verification of source documentation for each patient as well as other routine compliance reviews. The Sponsor's Medical Monitor and Pharmacovigilance Department will review safety data and be responsible for ensuring timely reporting of expedited SAERs to regulatory agencies and Investigators.

9.1.1 Good Clinical Practice

It is the responsibility of the Principal Investigator to oversee the safety of the patients at their site. The Investigator will ensure that this study is conducted in full compliance with the principles of the "Declaration of Helsinki" (as amended in Tokyo, Venice, Hong Kong, and South Africa), ICH guidelines, and with the laws and regulations of the country in which the research is conducted as applicable. By signing the US Form FDA 1572, "Statement of Investigator", the Investigator commits to adhere to applicable sections of the US CFR Title 21 Parts 50 "Protection of Human Patients", 56 "Institutional Review Boards", and 312 subpart D "Responsibilities of Sponsors and Investigators". All Investigators will ensure adherence to ICH guidelines for GCP and Clinical Safety Data Management, as well as all applicable laws and regulations, including US CFR Title 21 Part 54.

9.1.2 Institutional Review Board/Ethics Committee Approval

The Investigator shall assure that the IRB/EC will provide an initial and continuing review of the study. Prior to screening and enrollment of study patients, documented IRB/EC approval of the protocol, ICF and any patient materials must be obtained and provided to Spectrum or its designee.

9.1.3 Informed Consent

The Investigator is responsible for preparing the written Informed Consent document for this study. The Sponsor or its designee will provide the Investigator with an Informed Consent template. The Investigator may rearrange or reword the contents of the template, or may add other elements or language, provided the meaning and content are not changed or deleted. The Sponsor or designee is to review and approve the Informed Consent document that is used by the Investigator for this study prior to IRB/EC submission.

Written Informed Consent will be obtained from all patients participating in this study before any procedures are conducted, in accordance with ICH GCP and current regulatory requirements. The case history for each patient is to document that the Informed Consent process was obtained prior to participation in the study. The original Informed Consent document will be kept in the patient's record, and a copy will be provided to the patient.

9.1.4 Study Files and Retention of Records

The Investigator is to retain all study records until at least 2 years after the last approval of a marketing application in an ICH region and until there are no pending or contemplated marketing applications in an ICH region or at least 2 years have elapsed since the formal discontinuation of clinical development of the investigational product as per 21 CFR 312.62 and ICH GCP E6 4.9.5 and 5.5.12. These documents are to be retained for a longer period, however, if required by the applicable regulatory requirements or by an agreement with the Sponsor. It is the responsibility of the Sponsor to inform the Investigator when these documents no longer need to be retained. If the Investigator relocates, or for any reason desires to dispose of the records, the study records may be transferred to another institution, another investigator, or to the Sponsor upon written agreement between the Investigator and the Sponsor.

9.2 Recording and Collecting of Data

In accordance with ICH and GCP guidelines, the Investigator will maintain complete, accurate, legible, and easily retrievable data, and will allow personnel authorized by the Sponsor access to all study data at any time. Such data shall also be secured in order to prevent unauthorized access to data, or unauthorized editing or loss of data.

9.2.1 Case Report Forms

At scheduled monitoring visits, CRFs will be verified against source documentation and submitted as final data. Any subsequent changes to the CRFs are to be performed in accordance with the Sponsor's standard operating procedures for editing and clarifying CRFs. Data entry will be performed by the sites using an electronic data capture (EDC) system. Comment fields on the CRFs will be used as a means of clarification and communication between the Investigator and the Sponsor; however, comments entered in these fields will not be edited or clarified.

9.2.2 Drug Accountability

In accordance with all applicable regulatory requirements, the Investigator or designated site staff is to maintain study treatment accountability records throughout the course of the study. This person(s) will document the amount of poziotinib administered to patients. The CRA will review inventory and accountability documentation during monitoring visits.

The Investigator will not supply investigational study drugs to other investigators not listed on the US Form FDA 1572 or equivalent. Investigational study drug use, other than as directed by this protocol, is not allowed.

All unused vials of poziotinib are to be accounted for at the site and maintained in a secured, locked storage area with access limited to authorized study personnel only. Used poziotinib vials/bottles will be destroyed per institution, local, and all applicable policies and procedures. After study conclusion, all unused vials of poziotinib may be destroyed at the site, following verification of accountability by a Spectrum representative.

9.3 Protocol Compliance

The Principal Investigator is responsible for ensuring the study is conducted in accordance with the procedures and evaluations described in this protocol.

9.4 Sponsor Responsibilities

9.4.1 Safety Monitoring

The clinical drug safety of study treatment will be continuously evaluated by the study Medical Monitor or designee on an ongoing basis during the course of this clinical study. All SAEs related to study treatment in this study and all other ongoing clinical studies with study treatment will be processed in compliance with current regulatory guidelines by the Sponsor's Pharmacovigilance Department. This processing will include a formal assessment of each SAE by drug safety. In addition, a cumulative review of all SAEs from all sources will be assessed periodically.

9.5 Joint Investigator/Sponsor Responsibilities

9.5.1 Access to Information for Monitoring and Auditing

In accordance with ICH GCP guidelines and 21 CFR 312, the CRA/auditor is to have direct access to the patient's source documentation in order to verify the data recorded in the CRFs. The CRA is responsible for routine review of the CRFs at regular intervals throughout the study and to verify adherence to the protocol, as well as the completeness, consistency, and accuracy of the data being recorded. The CRA/auditor is to have access to any patient records needed to verify the entries on the CRFs, as well as access to all other study-related documentation and materials. The Investigator agrees to provide the monitor with sufficient time and facilities to conduct monitoring, and to cooperate with the monitor to ensure that any problems detected in the course of these monitoring/auditing visits are resolved.

9.5.2 Termination of the Study

For reasonable cause, either the Investigator or Spectrum may terminate the Investigator's participation in this study, provided a written notice is submitted within the time period provided for in the Clinical Trial Agreement (CTA). In addition, as per the terms mentioned in the CTA, the Sponsor may terminate the study at any time upon immediate notice for any reason, including but not limited to, Spectrum's belief that termination is necessary for the safety of patients.

9.5.3 Publication Policy

To coordinate the dissemination of data from this study, the Sponsor encourages the formation of a publication committee consisting of the principal investigator and appropriate Spectrum staff. The committee is expected to solicit input and assistance from other investigators and Sponsor staff as appropriate. Membership on the committee (both for investigators and Sponsor staff) does not guarantee authorship – the criteria described below should be met for every publication.

Authorship of any publications resulting from this study will be determined on the basis of the Uniform Requirements for Manuscript Submitted to Biomedical Journals (International Committee of Medical Journal Editors, 2005), which states:

- Authorship credit should be based on the following; authors should meet **all three** conditions:
 1. Substantial contributions to conception and design, acquisition of data, or analysis and interpretation of data
 2. Drafting the article or revising it critically for important intellectual content

3. Final approval of the version to be published

- When a large, multicenter group has conducted the work, the group should identify the individuals who accept direct responsibility for the manuscript. These individuals should fully meet the criteria for authorship defined above.
- Acquisition of funding, collection of data, or general supervision of the research group alone does not constitute authorship.
- All persons designated as authors should qualify for authorship, and all those who qualify should be listed.
- Each author should have participated sufficiently in the work to take public responsibility for appropriate portions of the content.
- All publications (e.g., manuscripts, abstracts, oral/slide presentations, books chapters) based on this study must be submitted to the Sponsor for corporate review.

9.6 Confidentiality

All information provided to the Investigator by the Sponsor, including nonclinical data, protocols, CRFs, information regarding poziotinib, and verbal and written information, will be kept strictly confidential and confined to the clinical personnel involved in conducting this study, and no disclosure shall be made except in accordance with the relevant CTA with Sponsor, including related to the confidentiality provisions and any right of publication granted to the Investigator in the CTA. All personnel will handle patient data in a confidential manner in accordance with applicable regulations governing clinical research and in accordance with the CTA. Upon request by a regulatory authority such as the US FDA and other regulatory authorities worldwide, the Investigator/institution is to make available for direct access all requested study-related records or reports generated as a result of a patient's participation in this study in accordance with the procedures and requirements of the CTA. This information may be related in confidence to the IRB/EC or other committee functioning in a similar capacity. In addition, no reports or information about the study or its progress will be provided to anyone not involved in the study other than to the Sponsor, or in confidence to the IRB/EC or similar committee, except if required by law and subject to the confidentiality and other provisions of the CTA.

b) Patients will be contacted by telephone on Days 3-8 and on Day 22 for assessment of adverse events.

c) An **End-of-Treatment Visit** will be performed 30 (±5) days after the last dose of poziotinib. An End of Study page will be recorded at that time.

d) A complete physical examination is required at **Screening, Day 1** of each Cycle, at Days 8 and 15 of Cycle 1, and at the **End-of-Treatment Visit**. Symptom-directed exams if clinically indicated are required at other visits.

- e) Pregnancy test (β -HCG) in women of child-bearing potential. Blood pregnancy test is required at **Screening**. Urine pregnancy test is required on Day 1 of each Cycle starting from **Cycle 2** and at **Cycle 1, Day 1**, if Screening pregnancy test was more than 7 days prior to **Day 1**. Urine pregnancy test also required at **End-of-Treatment Visit**.
- f) The **Screening** tumor assessment for patient eligibility will be based on scans performed within 30 days before the patient signed the ICF. Either CT, PET/CT, or MRI scans should be performed for non-brain organs and brain MRI scans should be performed locally per standard of care before the patient signed the ICF. **Baseline** tumor assessment (CT, PET/CT or MRI for non-brain and brain MRI) will be performed within 14 days prior to **Cycle 1, Day 1** and additional assessments will be made at 4 weeks (**Cycle 2, Day 1** [up to **Cycle 2, Day 7**]), at 8 weeks (**Cycle 3, Day 1** [up to **Cycle 3, Day 7**, with at least 28 days from previous tumor assessment]), and then every 8 weeks (± 7 days) thereafter until disease progression, death, intolerable adverse events (AEs), or other protocol-specified reasons for patient withdrawal.
- g) Tumor histopathology report (from local pathologist) and molecular test report for mutation diagnosis.
- h) Complete blood count (CBC), including white blood cells with 5-part differential, hemoglobin, and platelets, is to be obtained within 7 days prior to poziotinib administration on **Day 1** of each cycle, at which time, the patient's absolute neutrophil count $\geq 1.0 \times 10^9/L$ and platelet count $\geq 75 \times 10^9/L$ before administering the next dose of poziotinib. In addition, a CBC is to be performed on **Day 8** of **Cycles 1 and 2**.
- i) Blood for chemistry is to be collected within 7 days prior to poziotinib administration on **Day 1** of each Cycle.
- j) ECGs will be performed at screening. At select study centers, up to 25 patients may be specifically consented for ECG as defined below:
Schedule: A local 12-lead ECG will be obtained just before each PK blood sample on both Day 1 and Day 8. If the patient has interrupted continuous poziotinib dosing, clear dosing documentation must be done in order to assess suitability of further PK sampling and ECG recording.
- k) Cardiac ejection fraction may be evaluated at **Screening** in patients who are considered at high risk of cardiac disease, as determined by the Investigator, using echocardiogram or multi-gated acquisition (MUGA) scan. The investigator can order subsequent tests based on patient standard of care as determined by the Investigator.
- l) Tumor genotyping report from local lab is required to confirm patient mutation eligibility. Tissue sample (archival or fresh biopsy), if available, should be retained for retrospective analysis by FoundationOne CDx test. Collecting a tissue sample at progression is optional but is highly encouraged.
- m) Plasma samples will be required at **Screening** and optional on the day of each on-study imaging session, beginning at the 4-week imaging session, once every 8 weeks with imaging scan and when the patient progresses for biomarker analysis. Guardant's 360 or FoundationACT assays will be used, Plasma sample collection and storage will follow vendors' standard procedures as described in the vendors' Laboratory Manual.
- n) Whole blood samples will be drawn at **Screening** for pharmacogenomic analysis.
- o) At select study centers, up to 25 patients may be specifically consented for intensive PK sampling as defined below:
Schedule: Intensive PK blood sampling will be at pre-dose and 2, 4, 8, 12, and 24 hours post-dose on **Cycle 1, Day 1** and on **Cycle 1, Day 8 (± 3 days)**. The 12-hour and 24-hour PK samples must be collected prior to the second daily dose. If the patient has interrupted continuous poziotinib dosing, clear dosing documentation must be done in order to assess suitability of further PK sampling and ECG recording. In addition, if a patient presents with a potentially drug-related Grade ≥ 3 AE, a PK sample should be collected as soon as possible, if feasible, following the onset of the AE in order to characterize the PK. Documentation of last dose timing prior to the event is required.
- p) Poziotinib and loperamide will be dispensed on **Day 1** of each cycle. Patients will take poziotinib orally twice daily with food and a glass of water at approximately the same times each day. Loperamide will be given prophylactically for diarrhea as follows: 4 mg twice daily (bid) to three times daily (tid) or according to treating physician's instruction. .
- q) Adverse events will be assessed using National Cancer Institute Common Terminology Criteria for Adverse Events (CTCAE, version 5.0) and during **Screening** only study-related SAEs to be recorded.
- r) Weekly calls to patients will be conducted during the Days 3 to 8 of each cycle for the first 2 cycles as a follow up of expected adverse events.
- s) Patients who have consented will be contacted by phone (or email or letter if specifically requested) every 3 months, for up to 2 years after patient's first dose of poziotinib, for survival assessment.

**Appendix 2 EASTERN COOPERATIVE ONCOLOGY GROUP PERFORMANCE
STATUS SCALE**

[figure not shown]
Grade	ECOG Performance Status
0	Fully active, able to carry on all pre-disease performance without restriction.
1	Restricted in physically strenuous activity but ambulatory and able to carry out work of a light or sedentary nature, e.g., light house work, office work.
2	Ambulatory and capable of all self-care but unable to carry out any work activities. Up and about more than 50% of waking hours.
3	Capable of only limited self-care, confined to bed or chair more than 50% of waking hours.
4	Completely disabled. Cannot carry on any self-care. Totally confined to bed or chair.
5	Dead.

Appendix 3 DIARRHEA MANAGEMENT

RECOMMENDATIONS FOR DIARRHEA MANAGEMENT

For diarrhea management, the following interventions may be used based on the severity of the condition.

DIARRHEA SEVERITY	INTERVENTION

Start Diarrhea Prophylaxis *(CTCAE grade 0)
	
 - Start prophylactic therapy with Loperamide** 4mg orally twice daily when Poziotinib is initiated and continue for first 2 cycles - If patient becomes constipated, modify/discontinue Loperamide therapy appropriately - Upon development of diarrhea other etiologies including GI infection and inflammatory disorders must be ruled out. If Poziotinib related diarrhea is considered → follow the suggested approach per CTCAE severity as below:

Initiation of Poziotinib Treatment
	

Mild Diarrhea *(CTCAE Grade 1)
	
 - Continue Loperamide 4 mg orally, 3 times a day, followed by 2 mg every 4 hours or after each loose stool - Start Doxycycline at 100 mg orally (or alternatively use Minocycline 100 mg orally) twice a day, continue for 2 weeks or until resolution of diarrhea - Continue Poziotinib at the current dose level

Increase of <4 stools per day over baseline; mild increase in ostomy output compared to baseline
	

Moderate Diarrhea *(CTCAE Grade 2)
	
 - Continue Loperamide 4 mg orally, 3 times a day, followed by 2 mg every 4 hours or after each loose stool - Continue Doxycycline at 100 mg orally (or alternatively use Minocycline 100 mg orally) twice a day, continue for 2 weeks or until resolution of diarrhea - Consider starting Cholestyramine 4 g orally, once or a twice day (30 minutes prior to the meals), continue till improvement of diarrhea to Grade 1 or a resolution OR Budesonide orally 9 mg daily for 4 weeks - Continue Poziotinib at the current dose level

Increase of 4 - 6 stools per day over baseline; moderate increase in ostomy output compared to baseline; limiting instrumental ADL
	

Gastrointestinal disorders	*GRADE				
Adverse Event	1	2	3	4	5
Diarrhea	Increase of <4 stools per day over baseline; mild increase in ostomy output compared to baseline	Increase of 4 - 6 stools per day over baseline; moderate increase in ostomy output compared to baseline; limiting instrumental ADL	Increase of ≥7 stools per day over baseline; hospitalization indicated; severe increase in ostomy output compared to baseline; limiting self-care ADL	Life-threatening consequences; urgent intervention indicated	Death

Definition of Diarrhea: A disorder characterized by an increase in frequency and/or watery bowel movements.

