6.1.4 Poziotinib Dose Modification Recommendations

If needed, the initial dose (8 mg BID) may be reduced by 2 mg for each dose (ie 12 mg per day divided into 6 mg BID doses) at the Investigator's discretion and the Sponsor should be notified. If further dose reduction is required, the next dose should be reduced by a total of 2 mg/day (ie 10 mg per day divided into a 6 mg and 4 mg dose per day) and the Sponsor should be notified. Any further reductions in dose must be discussed a priori with the Sponsor's Medical Monitor and approval is required.

No dose reductions below 8 mg total dose/day are allowed.

Table 2 Poziotinib Dose Modifications Recommendations

Related Adverse Event	Grade	Occurrence	
		1	Each Additional Occurrence
Diarrhea	Grade ≥ 3 (Despite adequate anti-diarrhea management)	Stop poziotinib treatment until AE Grade ≤ 1 and then continue treatment at the same dose ^a or Reduce Poziotinib Dose by 2 mg/dose	Reduce Poziotinib Dose by ~1 mg/dose
	Grade ≥ 2 for ≥ 48 hours (Despite adequate diarrhea management)		
Fatigue	Grade ≥ 3		
Mucositis/ Stomatitis	Grade ≥ 3 (Despite adequate management)		
Nausea and/or Vomiting	Grade ≥ 3 (Despite adequate anti-emetics)		
	Grade ≥ 2 for ≥ 48 hours (Despite adequate anti-emetics)		
Rash	Any Grade	Refer to Appendix 4 .	

Related Adverse Event	Grade	Occurrence	
		1	Each Additional Occurrence
LVEF Dysfunction	Grade ≥ 3	Discontinue Treatment	

- a) Supportive medications, including early steroid use, should be considered even in the presence of low-grade “on-target” toxicity (eg, rash, diarrhea)(Appendix 4).

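### For Grade 2 diarrhea lasting 48 hours or more despite management, Table 2 calls for a dose hold or reduction while Appendix 3 says to continue at the current dose

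*Combined protocol and SAP*

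**What the plan says.** Table 2 appears twice with the same content, once in the Synopsis and once in Section 6.1.4. One of its two diarrhea rows covers Grade 2 or higher lasting at least "48 hours (Despite adequate diarrhea management"). The first-occurrence cell begins "Stop poziotinib treatment until AE Grade" 1 or lower, followed by continuation at the same dose, and then offers an alternative: "or Reduce Poziotinib Dose by 2 mg/dose". For each further occurrence the cell reads "Reduce Poziotinib Dose by ~1 mg/dose".

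Appendix 3 sets out diarrhea management by CTCAE grade. Its Grade 2 row lists loperamide, doxycycline or minocycline, and optionally cholestyramine or budesonide, and ends with a dose instruction: "Continue Poziotinib at the current dose level". The row sets no time limit on that instruction and does not mention Table 2.

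Three other places bear on which text governs:

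- Section 7.1 has the investigator base dose modification on the rules in Section 6.1.4.
- Section 5.4.11.2.1 lists the Appendix 3 algorithm as one of three ways to manage diarrhea, beside investigator standard of care and institutional guidelines. Appendix 3 says of itself that "the following interventions may be used based on the severity of the condition".
- Section 5.3.3, on the telephone contact between Days 3 and 8 of Cycle 1, tells sites to act on adverse events such as diarrhea according to Appendices 3, 4 and 5.

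**The concern.** Appendix 3 goes beyond supportive care, because its Grade 2 row also says what to do with the study drug. For Grade 2 diarrhea that persists under treatment, that instruction differs from every action in Table 2. A site working from the appendix leaves the dose unchanged, while a site working from Section 6.1.4 interrupts or reduces it.

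The first thing at stake is safety management of an event that Section 7.2 names as an adverse event of special interest. The second is interpretation of exposure. Section 8.6 plans a summary of relative dose intensity for each cohort. If handling differs between sites, some of the variation in that summary will reflect which page a site followed and not tolerability. The study plans about 25 centers and cohorts of 9 patients at the first stage and 30 in total, so a few patients handled differently could shift a cohort's summary.

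**Working it through.** No figure in the plan needs to be reproduced; the check is a comparison of texts. Take a patient with continuous Grade 2 diarrhea, treated adequately, at hour 49.

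| Situation | Table 2 (Synopsis and Section 6.1.4) | Appendix 3, Grade 2 row |
|---|---|---|
| First occurrence | Hold to Grade 1 or better and resume at same dose, or reduce by 2 mg per dose | Continue, same dose |
| Each later occurrence | Reduce by about 1 mg per dose | Continue, same dose |

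1. *Does the Table 2 row apply?* Yes: the grade, the duration and the condition "Despite adequate diarrhea management" are all met. In the text read for this review the action cells are merged across rows. Reading them as applying to this row is the only sensible reading, since the row would otherwise have no action.
2. *Does the Appendix 3 row apply?* Yes. It is keyed to grade alone. It also envisages treatment well past 48 hours: doxycycline for 2 weeks or until resolution, and "Budesonide orally 9 mg daily for 4 weeks".
3. *Does any Table 2 action agree with Appendix 3?* No. Even the first-occurrence option that keeps the dose level interrupts dosing, and the other options lower the dose.
4. *Does a cross-reference settle it?* No. The rash row of Table 2 points to Appendix 4, but the diarrhea rows point to no appendix. The table's footnote mentions diarrhea but cites Appendix 4, the rash appendix. The Grade 2 row of Appendix 3 does not mention Table 2.
5. *Do other sections settle it?* In part. Section 7.1 favors Section 6.1.4, and Section 5.4.11.2.1 makes Appendix 3 optional, but Section 5.3.3 directs sites to Appendix 3 without that qualification.

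The size for one patient can be illustrated. Assume the patient is on the starting dose of 8 mg twice daily, 2 × 8 = 16 mg per day. The 2 mg per dose reduction gives 2 × 6 = 12 mg per day, the figure stated in Section 6.1.4. The difference from continuing is (16 − 12)/16 = 25% of the daily dose for as long as the reduction lasts. Under the hold option, the difference is the dose missed during the hold, whose length the documents do not predict.

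**The case against.** The strongest reply is that precedence is already set. Section 7.1 names Section 6.1.4 as the basis for dose decisions, while Appendix 3 is optional both by its own wording and by Section 5.4.11.2.1. A sequential reading is also available: begin the Appendix 3 measures at the current dose and turn to Table 2 if they fail for 48 hours. That reading is coherent, and many investigators would probably adopt it. It softens the conflict without removing it, because Appendix 3 gives its own dose instruction, never says that it yields after 48 hours, and is the place to which Section 5.3.3 sends sites. Nor does the protocol say when management counts as adequate, so sites could place the handover at different times.

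Other parts of the reply stand. The treatment periods of 2 and 4 weeks are courses of supportive drugs, not durations of Grade 2 diarrhea; they show only that the row is not confined to the first 48 hours. Some variation between sites is permitted anyway, by the choice within Table 2 and by the options in Section 5.4.11.2.1. The text available shows Appendix 3 rows only up to Grade 2; higher-grade rows may have been lost in conversion from PDF, and nothing here relies on their absence.

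A reader might infer that Table 2 requires a stop, so that one page says stop and the other says continue. The documents do not support that: the table is headed as recommendations, its first-occurrence cell also offers a reduction, and later occurrences call for reduction.

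**Conclusion.** The protocol is wrong as written on this point: it contradicts itself on the dose for Grade 2 diarrhea lasting 48 hours or more despite adequate management. The conclusion rests on the wording of the two passages and on the merged action cells of Table 2 applying to the 48-hour row. The consequences for safety management and relative dose intensity are plausible but not quantified in the documents.

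The number of patients affected cannot be stated. A reader might be tempted to apply the diarrhea rates in Section 1.1.2.5.2, 73.7% to 87.9%, to the planned 150 patients: 0.737 × 150 ≈ 111 and 0.879 × 150 ≈ 132. Those figures do not measure this problem. They count diarrhea without regard to grade or duration, they come from other studies in breast and lung cancer, and the same section reports better tolerability with 8 mg twice daily than with 16 mg once daily. They also assume that every cohort passes its first stage. Under the null response rate, the plan's own expected size is 16.76 per cohort, or 5 × 16.76 ≈ 84 in all.

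A reader might also infer that Table 2 is the correct rule and Appendix 3 the error. Section 7.1 points that way for dose decisions, but Section 5.3.3 points to the appendix, and which instruction is clinically right is not a question this review answers.

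**What to change.** Reconcile the Grade 2 row of Appendix 3 with the diarrhea rows of Table 2, in both the Synopsis and Section 6.1.4, so that the protocol gives one consistent dose instruction for Grade 2 diarrhea lasting 48 hours or more despite adequate management. Add a cross-reference in each direction, and check that Sections 5.3.3 and 5.4.11.2.1 agree with the result. The choice of instruction belongs to the sponsor's clinical team.

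The cost is about one line in Appendix 3 and a short pointer in each copy of Table 2. No change to the design, sample size or analysis is needed.
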